2.1. Multiplicity Adjustment

No multiplicity adjustment is planned for this study.

3. ANALYSIS SETS

Analysis Set	Definition / Criteria	Analyses Evaluated
Screened	All participants who were screened for eligibility.	
 • Study Population
Enrolled	
All participants who entered the study.
 
Note: screening failures (who never passed screening even if rescreened) are excluded from the Enrolled analysis set as they did not enter the study.
	
 • Study Population (Part C)
Randomized	All participants who were randomly assigned to study intervention.	
 • Study Population (Part A)
Safety	All randomized (Part A)/ enrolled (Part C) participants who were exposed to study intervention. Participants will be reported according to the intervention they actually received.	
 • Safety • Study Population • PRO Assessments • CCI [REDACTED]
Pharmacokinetic (PK)	
All participants in the Safety analysis set who had at least 1 non-missing PK assessment – i.e., PK sample collected and analyzed. Note: Non-quantifiable [NQ] values will be considered as non-missing values.
 
Participants will be reported according to the intervention they actually received.
	
 • PK • Safety
PK Principal Stratum	All participants in the PK analysis set who would be able to complete the IM/IV dose. Participants will be reported according to the treatment arm they actually received.	
 • PK • Safety

4. STATISTICAL ANALYSES

4.1. General Considerations

4.1.1. General Methodology

All data will be reported for each study part separately, and separately for each Cohort within Part C. The data will be listed and summarized according to GSK reporting standards, where applicable. In summary tables, results will be presented by treatment arms. The treatment display format is specified in (OPS) Section 4.2.1 Study Treatment Display Descriptors.

Confidence intervals will use 95% confidence levels unless otherwise specified.

Unless otherwise specified, endpoints defined in Section 1.1 will be summarized using descriptive statistics, graphically presented (where appropriate) and listed. Continuous data (except for PK concentration data) will be summarized using n, mean, standard deviation (SD), median, minimum and maximum; for PK concentration data, between-subject CV (%CV_b), 95% CIs, 5th and 95th percentiles will also be reported along with above mentioned summary statistics; categorical variables will be summarized using n and percentage of participants in each category; log_e-transformed serum concentration and PK parameters will be summarized using geometric mean, 95% CI, SD (logs) and the %CV_b based on geometric mean. To assess relative bioavailability, log_e-transformed PK parameters will be statistically analyzed separately using Analysis of covariance (ANCOVA) Model to report point estimate for the ratio of the geometric means of treatment groups under comparison along with 90% CI.

In the case of a difference between the stratification assigned at the time of randomization and the data collected in the electronic case report form (eCRF), the analyses will be performed based on the data collected in the eCRF, not the assigned stratum at randomization.

For all study parts, JSRT will review safety data at regular intervals as described in the JSRT charter. During review of the Part A Sentinel cohort, the JSRT will review the participant data after all of the arms within a study Part have approximately 5 participants who have completed at least Day 8. This will include at least AE, SAE, AESI (including injection site reactions [ISRs]) and safety lab results. In Part A, an interim analysis (IA) will be conducted to review Part A data and decide whether to open Part B and, if needed, the selection treatment arms Part B; In Part C, an IA will be performed to support periodic data reviews across the program. Refer to Section 4.5 for more details.

4.1.2. Baseline and Post-Baseline Definition

For all endpoints (except for electrocardiogram [ECG]) the baseline value will be the latest pre-dose assessment with a non-missing value on or after Day -1 visit, including those from unscheduled visits. For ECG endpoints, which pre-dose measurements are only planned at Screening visit, the baseline value will be the most recent pre-dose assessment with non-missing value before Day 1 visit, including unscheduled visits. If triplicate 12-lead ECGs are collected at the last pre-dose assessment, the average of the

three measurements will be used as baseline record. If time is not collected, Day 1 assessments are assumed to be taken prior to first dose and used as baseline. If triplicate 12-lead ECGs are collected at any post-baseline visit, the average of the three measurements will be calculated and used in derivation of summary statistics.

Unless otherwise stated, if baseline data is missing no derivation will be performed and baseline will be set to missing.

Post-Baseline is defined as an occurrence after first dose of the treatment on Day 1.

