1.3. Schedule of Activities (SoA)

Table 1 Schedule of Activities: Part A and Part B

Study Visit Day ± Visit Window	Screening ¹ (up to Day -28)	W1			W2	W3	W4	W8	W12	W20	W24	W35	Notes ¹⁶	
		Day -1	Day 1	Day 2	Day 3	Day 5±1d	Day 8±1d	Day 15±1d	Day 29±2d	Day 57±4d	Day 85±7d	Day 140±7d	Day 168±7d	
Site visit (S), home visit (H), or call (C)	S	S	S	S	S	S	S	S	S/H	S/H	S/H	S/H	C	NOTE: Whenever vital signs, 12-lead ECGs, and blood draws are scheduled for the same nominal time, the assessments should occur in the following order: vital signs, 12-lead ECG, and blood draws. The timing of the assessments should allow the blood draw to occur at the exact nominal time. The actual time of assessment or procedure must be reported in the eCRF.
Informed consent	X													1. All screening procedures must be completed within 28 days prior to dosing.
Demographics	X													2. Provide details of any changes to medical history since Screening.
Medical history (including medication/drug/alcohol/tobacco use, allergies, illnesses, and SARS-CoV-2 infection/therapy/vaccination)	X	X ²												3. Including height and weight.
Randomization			X											4. Record Day 1 vital signs within 1 hour prior to dosing, and immediately after injections. Vital signs will be monitored at approximately 15 minutes, 30 minutes, and 1 hour after dosing. Vital signs on other days should be performed once at any time of the day.
Study intervention administration			X											5. Local injection site tolerability assessment on Day 1 at approximately 15 minutes, 30 minutes, and 1 hour post-dose and on Day 2, Day 3, Day 5, and Day 8. All ISRs need to be followed by the PI to resolution.
Assessments	Complete (C) or brief (B) physical examination	C ³	B	B	B									6. Triplicate 12-lead ECGs will be collected at Screening.
	Vital signs (BP, PR, RR, temperature, SpO ₂) ⁴	X	X ⁴	X	X	X	X	X	X	X	X	X	X	7. On Day 1, PIN_TS3.0 assessment will be performed before bedtime (at home). Assessments on Days 2, 3, 5, and 8 will be performed when participants arrive at the site.
	Local injection site tolerability assessment		X ⁵	X ⁵	X ⁵	X ⁵								8. On Day 1, Pain-NRS will be assessed at 15 minutes, 30 minutes, and 1 hour after dosing (at site) and before bedtime (at home). Assessments on Days 2, 3, 5, and 8 will be performed when participants arrive at the site.
	12-lead ECG	X ⁶												9. Baseline laboratory assessments should be collected on Day -1.

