8. STUDY ASSESSMENTS AND PROCEDURES

- Study procedures and their timing are summarized in the SoA (Section 1.3). Whenever vital signs, 12-lead ECGs, and blood draws are scheduled for the same nominal time, the assessments should occur in the following order: vital signs, 12-lead ECG, blood draws. The timing of the assessments should allow the blood draw to occur at the exact nominal time. The actual time of assessment or procedure must be reported in the eCRF.
- Protocol waivers or exemptions are not allowed.
- Immediate safety concerns should be discussed with the Medical Monitor immediately upon occurrence or awareness to determine if the participant should continue or discontinue study intervention.
- Adherence to the study design requirements, including those specified in the SoA (Section 1.3), is essential and required for study conduct.
- All screening evaluations must be completed and reviewed to confirm that potential participants meet all eligibility criteria. The investigator will maintain a screening log to record details of all participants screened and to confirm eligibility or record reasons for screening failure, as applicable.

- CC1

- Procedures conducted as part of the participant's routine clinical management (e.g., blood count) and obtained before signing of ICF may be utilized for screening or baseline purposes provided the procedure met the protocol-specified criteria and was performed within the timeframe defined in the SoA (Section 1.3).
- The maximum amount of blood collected from each participant over the duration of the study, including any extra assessments that may be required, will not exceed 500 mL. Typical blood volumes expected during the usual course of study participation will be approximately 150 mL.
- Repeat or unscheduled samples may be taken for safety reasons or for technical issues with the samples.

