6.2. Appendix 1 Data Derivations Rule

6.2.1. Change from Baseline

The change from baseline will be calculated by subtracting the baseline values from the individual post-baseline values. If either the baseline or post-baseline value is missing, the change from baseline is set to missing as well.

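### Does the rule for untimed Day 1 readings let post-dose values become baseline, and does the ECG findings summary overlook Part C?

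*SAP*

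**What the plan says.** **Baseline.** For everything except ECGs, SAP section 4.1.2 takes the last non-missing pre-dose value from Day -1 onward. For ECGs it states: "For ECG endpoints, which pre-dose measurements are only planned at Screening visit", and then "the baseline value will be the most recent pre-dose assessment with non-missing value before Day 1 visit". The fallback follows: "If time is not collected, Day 1 assessments are assumed to be taken prior to first dose and used as baseline". The section closes with: "Post-Baseline is defined as an occurrence after first dose of the treatment on Day 1". SAP section 6.2.1 applies the result: "The change from baseline will be calculated by subtracting the baseline values from the individual post-baseline values".

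**Timing of Day 1 vital signs.** Note 4 to the Part A and B schedule (protocol section 1.3) reads "Record Day 1 vital signs within 1 hour prior to dosing, and immediately after injections" and "Vital signs will be monitored at approximately 15 minutes, 30 minutes, and 1 hour after dosing". Protocol section 8 adds: "The actual time of assessment or procedure must be reported in the eCRF".

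**ECG findings.** SAP section 4.3.2.3 ranks findings in three classes (normal; abnormal without clinical significance; abnormal with it), takes the worst at each time point when an ECG is repeated, and names the Screening visit for the summary of findings. The same section tabulates QTcF by category, defines a worst post-baseline QTcF, and lists both abnormal values of potential clinical importance and clinically significant findings.

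**The concern.** The fallback is not expressly limited to assessments planned before dosing, and it does not say that a timed pre-dose reading outranks an untimed one. Day 1 of Part A has more vital-sign sets after dosing than before. Taken literally, an untimed set from 30 minutes after injection could count as pre-dose and, being the latest, become baseline. That would contradict the section's own definition of post-baseline. One misplaced baseline alters every later change for that participant and that test, and clinically significant vital-sign change from baseline is a listed safety endpoint (SAP sections 1.1 and 4.3.2.2). The sentence also sits between two ECG sentences. If it covers ECGs, it clashes with a rule that takes ECG baseline only from before the Day 1 visit.

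The ECG findings summary raises a separate worry. Naming Screening fits Part A, where that is the only scheduled ECG. Part C has later ECGs and gives a dose and infusion rate not used before, so a table confined to Screening would show nothing about findings after the infusion.

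**Working it through.** The plan gives no figure to reproduce. The check compares the passages and then bounds the possible effect.

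**1. What the fallback governs.** Section 4.1.2 uses missing and non-missing for absent values, but here it speaks of time not being collected. The natural reading is a data item whose form records a date and no clock time. For such items the assumption is sensible: the Day 1 immunogenicity sample, for example, is scheduled before dosing (note 14 to the Part A and B schedule). Vital signs are different, because protocol section 8 requires their actual times.

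**2. If a vital-sign time is nevertheless blank.** The governing rule still asks for the latest pre-dose value, and post-baseline means after the first dose. A set planned for 15 minutes, 30 minutes or 1 hour after dosing is identified as post-dose by its planned time point. Section 4.3.1.3 of the SAP already summarises concentrations by nominal time, so the device is familiar to the analysts.

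**3. Size under assumed rates.** Inputs: 190 Part A participants (protocol section 9.5); 1 pre-dose and 4 post-dose Day 1 sets (note 4), so 5 in all. Assumption, with no source in the documents: each set lacks a time independently with probability q, and no set is missing altogether.

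- Worst reading, in which any untimed post-dose set displaces a timed pre-dose set: P = 1 − (1 − q)^4.
  - q = 0.1%: P = 0.399%; 190 × P = 0.76
  - q = 0.5%: P = 1.985%; 190 × P = 3.77
  - q = 1%: P = 3.940%; 190 × P = 7.49
- Ordinary reading, in which a timed pre-dose set is kept, so the pre-dose set must be untimed as well: P = q × [1 − (1 − q)^4].
  - q = 0.1%: 0.0008 of 190
  - q = 0.5%: 0.019 of 190
  - q = 1%: 0.075 of 190

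The first set of results needs analysts to discard a timed pre-dose value in favour of one scheduled after dosing. The second is effectively nobody.

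**4. The ECG baseline.** In Part A the clash cannot arise from scheduled ECGs, since none falls on Day 1. In Part C the ECG row carries four marks, but its columns are not reliably readable, so the days cannot be stated. If one later mark is Day -1, the rule already selects it as the most recent before Day 1. If one is Day 1 pre-dose, the rule uses an earlier pre-dose value instead. Under that specific ECG rule, baseline remains a genuine pre-dose reading.

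**5. The ECG findings summary.** Four marks less Screening leaves three Part C time points. If each mark is a separate visit, the earliest possible placement is Screening, Day -1, Day 1 and then Day 2 or later, so at least one is post-dose. Against that:

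- post-baseline triplicates are averaged and enter the summary statistics (SAP sections 4.1.2 and 6.2.5);
- worst post-baseline QTcF is derived, and QTcF categories are not confined to Screening (section 4.3.2.3);
- clinically significant findings are listed, and ECG abnormalities judged clinically significant are adverse events (protocol section 10.3.1), so they enter the primary safety summaries;
- ECG is not among the endpoints in SAP sections 1.1 or 4.3.2.2.

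What is left is a by-visit count of findings, chiefly abnormalities judged not clinically significant.

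**The case for a change.** The strongest case for a change is that both points are textual facts and cheap to settle. The fallback has no stated scope and no tie-break, and step 3 shows that the tie-break separates a handful of participants from none. The Screening wording does not match the SAP's own provisions for post-baseline ECGs, and Part C exists to characterise safety at a new dose and infusion rate. Two sentences and at most one table, from data already collected, would remove the ambiguity.

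Part of this stands. The fallback could be worded more tightly, and the ECG sentence looks carried over from Part A. The statement that pre-dose ECGs are planned only at Screening may also not hold for Part C, which the readable schedule cannot settle. But the case does not show a result that would come out differently. The larger counts rest on assumed rates and on a choice a competent programmer would not make. The Screening sentence does not exclude other visits, and the SAP leaves its displays to the output and programming specification, which is not among the documents. The absence of a Part C findings table is therefore not established.

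**Conclusion.** No change to the plan follows. The Day 1 fallback is a date-only convention that analysts can apply sensibly from the surrounding definitions and the planned time points. On that reading the expected effect is below 0.1 of 190 Part A participants even at an assumed 1% of sets without a time. The upper bound of 0.8 to 7.5 participants applies only if timed pre-dose readings are overwritten. It would touch descriptive vital-sign changes and no primary endpoint.

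The ECG wording leaves at most one descriptive display unnamed in the SAP text, for data that are already handled through QTcF, listings and adverse events.

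This conclusion assumes that actual times are recorded as the protocol requires, that each reading can be linked to its planned time point, and that clinically significant ECG abnormalities are reported as adverse events. The primary PK ratios, their precision, and the primary incidence of adverse events do not depend on either sentence.

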4.2. Primary Endpoint(s)/Estimands Analyses

4.2.1. Pharmacokinetics

4.2.1.1. Estimands

Table 1 Primary Estimand for Primary Pharmacokinetics Endpoint (Part A)

Primary Estimand	
Population	Male or female healthy participants aged 18 to 65 years who would be able to complete the IM dose
Variable/Endpoints	Sotrovimab serum PK parameters: AUC_{D1-29} and C_{max}
Treatment	100 mg/mL IM sotrovimab vs 62.5 mg/mL IM sotrovimab (dorsogluteal injections)
Strategy for Intercurrent Events or Events Leading to Missing Data	The intercurrent event of interest is participants receiving an incomplete IM dose. The strategy for handling this intercurrent event will be a Principal Stratum Strategy, where we are only interested in the strata of participants who would be able to receive a complete IM dose. Exclusion of participants who did not receive a complete IM dose will not introduce bias as the reasons for dose interruption are not related to their PK.
Population-Level Summary	The point estimate for the ratio of the geometric means of 100 mg/mL treatment group compared to the 62.5 mg/mL treatment group and the related 90% CI will be calculated.

Log-transformed parameters (AUC_{D1-29} and C_{max}) will be compared between treatment groups using ANCOVA models that include all four treatment groups, sex, and BMI (in kg/m^2) as variables. Least square estimates of treatment differences (contrasts for each comparison of interest) will be back-transformed to estimate relative bioavailability with two-sided 90% CIs. This analysis will be based on the PK Principal Stratum Analysis Set in Part A.

4.2.1.2. Definition of Endpoint(s)

Relative bioavailability comparisons (100 mg/mL IM sotrovimab at the dorsogluteal injection site relative to the 62.5 mg/mL formulation administered dorsogluteally) will be performed upon availability of PK data up to Day 29 for Part A.

4.2.1.3. Main Analytical Approach

Relative Bioavailability Assessment	
Endpoint(s)	

 • C_{max}, AUC_{D1-29} 	
Model Specification	

 • \log_e-transformed value of endpoints will be statistically analyzed separately using analysis of covariance (ANCOVA) with the following terms: 
 ○ Dependent variable: C_{max}, AUC_{D1-29} ○ Covariates: sex, baseline BMI, treatment (62.5 mg/mL IM sotrovimab into dorsogluteal muscles, 100 mg/mL IM sotrovimab into dorsogluteal muscles, 100 mg/mL IM sotrovimab into anterolateral thigh and 100 mg/mL IM sotrovimab into deltoid) 	

Data will be analyzed for PK Principal Stratum Analysis Set in Part A.
 
 • The analysis will be performed using the mixed linear model procedure within the SAS/STAT module of the SAS system. • Point estimates and their associated 90% CIs will be constructed for the differences in PK parameter values between 100 mg/mL sotrovimab (dorsogluteal muscles) and 62.5 mg/mL sotrovimab (dorsogluteal muscles). The point estimates and their associated 90% CIs will then be back transformed to provide point estimates and their 90% CIs for the ratios, test/reference in PK parameter values on the original scale. • The Kenward and Roger method for approximating the denominator degrees of freedom and correcting for bias in the estimated variance-covariance of the fixed effects will be used. 	
Model Checking & Diagnostics	

 • For ANCOVA, model assumptions will be checked, and appropriate adjustments may be applied based on the data. • Distributional assumptions underlying the model used for analysis will be examined by obtaining a normal probability plot of the residuals and a plot of the residuals versus the fitted values (i.e., checking the normality assumption and constant variance assumption of the model respectively) to gain confidence that the model assumptions are reasonable 	
Model Results Presentation	

 • Geometric least-squares means for each treatment arm (100 mg/mL and 62.5 mg/mL IM sotrovimab [dorsogluteal], respectively), point estimates and associated 90% CIs for the ratios for each parameter will be produced in tabular format. • Plots of geometric mean ratio of test to reference treatment arm (100 mg/mL IM sotrovimab vs. 62.5 mg/mL IM sotrovimab [dorsogluteal]) together with 90% CIs will be produced. 	

4.2.2. Safety

4.2.2.1. Estimands

Table 2 Primary Estimand of the Primary Safety Endpoint

Part A:

Primary Estimand	
Population	Male or female healthy participants aged 18 to 65 years
Variable/Endpoints	Incidence of all AEs, SAEs, and AESI through Day 29 (i.e., all events on the database at the time of DCO)
Treatment	100 mg/mL IM sotrovimab and 62.5 mg/mL IM sotrovimab (dorsogluteal injections)
Strategy for Intercurrent Events or Events Leading to Missing Data	The intercurrent event of interest is participants receiving incomplete IM dose. The strategy for handling this intercurrent event will be a Treatment Policy Strategy, where all safety data after the intercurrent event will be included. Missing data will not be imputed.
Population-Level Summary	Frequency and percentages of participants

Part C Cohort 1:

Primary Estimand	
Population	Male or female healthy participants aged 18 to 65 years
Variable/Endpoints	Incidence of all AEs, SAEs, and AESI through Day 29 (i.e., all events on the database at the time of DCO)
Treatment	Single IV infusion of sotrovimab at 3000 mg dose.
Strategy for Intercurrent Events or Events Leading to Missing Data	The intercurrent event of interest is participants receiving incomplete IV dose. The strategy for handling this intercurrent event will be a Treatment Policy Strategy, where all safety data after the intercurrent event will be included. Missing data will not be imputed.
Population-Level Summary	Frequency and percentages of participants

4.2.2.2. Definition of Endpoint(s)

The primary safety endpoints for the primary safety objectives (Part A: safety and tolerability of 100 mg/mL and 62.5 mg/mL IM sotrovimab at the dorsogluteal injection sites; Part C: safety and tolerability of IV sotrovimab) are:

- Incidence of AEs through Day 29
- Incidence of SAEs through Day 29
- Incidence of AESIs through Day 29

4.2.2.3. Main Analytical Approach

The analyses described in the following sections, will be performed using the Safety analysis set in all study parts, as defined in Section 3. Unless otherwise specified, available data will be analyzed as collected regardless of intercurrent events that may occur (treatment policy). Missing data will not be imputed.

Incidence of AEs, SAEs, and AESIs through Day 29 will be displayed in the form of summaries and listings, where appropriate. Further details are provided below.

Adverse Events

Adverse events will be coded using Medical Dictionary for Regulatory Activities (MedDRA) central coding dictionary. Adverse events analyses including the analysis of AEs, SAEs and other significant AEs will be based on GSK Core Data Standards.

Adverse event displays to be generated include: overview of AEs, all AEs, all SAEs, AEs leading to permanent discontinuation of study treatment or permanent withdrawal from study, common ($\geq 5\%$) AEs, common ($\geq 5\%$) Non-Serious AEs, common ($\geq 5\%$) SAEs, Drug-related AEs, Serious Drug-related AEs, Non-Serious Drug-related AEs, and Adverse events leading to withdrawal. For Part C, common ($\geq 1\%$) AEs, common ($\geq 1\%$) Non-Serious AEs, common ($\geq 1\%$) SAEs may be additionally reported. The number and percentages of participants with the event will be summarized by System Order Class (SOC) and Preferred Term (PT), unless otherwise specified in the [OPS](#). Adverse Events including fatal SAEs and AEs leading to withdrawal will also be listed as specified in the [OPS](#).

A drug-related AE is defined as an AE for which the investigator classifies the relationship to study intervention as “Yes”. A worst-case scenario approach will be taken to handle missing relatedness data, i.e. the summary table will include events with the relationship to study intervention as ‘Yes’ or missing.

Adverse Events of Special Interest

Adverse events of special interest will be monitored by GSK at Day 29 and either during or at the end of the study (through Week 35). These will be updated during the course of the study based on accumulating safety data.

Adverse event of special interest includes:

- Hypersensitivity reactions occurring any time post dose

- Infusion-related reactions within 24 hours post dose (Part C)
- Injection site reactions (Part A)
- Immunogenicity
- AEs potentially related to antibody-dependent enhancement of disease

AESI of hypersensitivity reactions occurring any time post dose, infusion-related reactions within 24 hours post dose and injection site reactions will be recorded in CRF. For reporting purposes, the MedDRA SMQs or HLTs will be used if applicable or custom list of PTs as agreed with JSRT and aligned with current MedDRA version at the time of reporting. For each of these AESI, the number and percentages of participants with the event will be summarized. Events will be summarized by PT, unless otherwise specified in the [OPS](#). For AESI of injection site reactions (applicable to IM route of administration only), in addition, a cumulative distribution curve of time to first injection site reaction will be produced for each treatment arm.

AEs potentially related to immunogenicity will be reviewed directly from the overall subject anti-drug antibody and AE listings and will be detailed in the CSR. AEs potentially related to antibody-dependent enhancement will be reviewed directly from the COVID-19 infected participants and AE listings and will be detailed in the CSR.

